7.9.2.3. Change from Baseline in Adapted Pain and Function Subscale

MMRM will be performed to estimate change from baseline treatment effect at Day 22, 43, 64 and Day 95 Visits comparing active to placebo for adapted pain subscale and adapted function subscale in the affected shoulder. MMRM will be performed to estimate the LS means of change from baseline for EN3835 and placebo treatment. *P* values and 95% CIs for the treatment difference (EN3835 – Placebo) will be calculated by MMRM for the visits with treatment, visit, and an interaction of treatment and visit as fixed effected and repeated with visit/subject. Autoregressive covariance structure will be used in the model.

Observed values and change from baseline in adapted pain subscale and adapted function subscale in the affected shoulder for each treatment group will be summarized at Day 22, 43, 64, and 95 Visits using descriptive statistics.

In addition, score and change from baseline for each of the individual questions will be summarized for adapted function subscale for each treatment group using frequency counts and percentages with mean and SD.

7.9.2.4. Change from Baseline in PUM Scale

MMRM will be performed to estimate change from baseline treatment effect at Day 64 and Day 95 Visit comparing active to placebo for PUM scale in the affected shoulder. MMRM will be performed to estimate the LS means of change from baseline for EN3835 and placebo treatment. *P* values and 95% CIs for the treatment difference (EN3835 – Placebo) will be

25-April-2022

calculated by MMRM for the visits with treatment, visit, and an interaction of treatment and visit as fixed effected and repeated with visit/subject. Autoregressive covariance structure will be used in the model.

Observed values and change from baseline in the PUM scale in the affected shoulder for each treatment group will be summarized at Day 64 and Day 95 Visits using descriptive statistics.

A listing of PUM scale scores will be provided.

7.9.2.5. Change from Baseline in Patient-reported Global Severity of Adhesive Capsulitis Scale

A Wilcoxon rank sum nonparametric test will be used to compare EN3835 to placebo for the change from baseline in Patient-reported Global Severity of Adhesive Capsulitis Scale in the affected shoulder at the Day 22, 43, 64 and 95 Visits.

The null and alternative hypotheses for this test will be as below:

H₀: There is no difference in the change in severity in the 2 treatment groups.

Vs

H₁: The change in severity differs in the 2 treatment groups.

The Wilcoxon scores (Rank Sums) for treatment groups and test statistics along with p value for the test of significance will be presented.

Observed values and change from baseline in Patient-reported Global Severity of Adhesive Capsulitis Scale in the affected shoulder for each treatment group will be summarized at the Day 22, 43, 64 and 95 Visits using descriptive statistics.

A listing of Patient-reported Global Severity of Adhesive Capsulitis Scale scores will be provided.

7.9.2.6. Patient-reported Change in Severity of Adhesive Capsulitis Scale

Reponses for Patient-reported Change in Severity of Adhesive Capsulitis Scale at the Day 22, 43, 64, and 95 Visits will be compared between EN3835 to placebo using a chi-square test (or Fisher's exact test based on expected frequencies).

The null and alternative hypotheses for this test will be as below:

H₀: The distribution of responses is independent of the treatment groups.

Vs

H₁: The distribution of responses is dependent on the treatment group (ie, there is a difference in distribution of responses among the treatment groups).

Reponses for Patient-reported Change in Severity of Adhesive Capsulitis Scale will be summarized by each treatment group using frequency counts and percentages and in addition chi-square (or Fisher's exact) test statistics along with *p* value for the test of significance will be presented.

The change in the symptoms will be summarized by each treatment group using frequency counts and percentages with mean and SD.

25-April-2022

A listing of Patient-reported Change in Severity of Adhesive Capsulitis Scale scores will be provided.

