9.3.1. Efficacy Analysis

The primary endpoint is the change from baseline to the Day 95 Visit in the adapted ASES composite score.

A mixed-model ANOVA with factors for treatment group and visit will be performed to compare active to placebo for the change from baseline to the Day 95 Visit in adapted ASES composite score.

A mixed-model ANOVA with factors for treatment group and visit will be performed to compare active to placebo for the absolute and percent change from baseline to the Day 22, 43, 64, and Day 95 Visits in PROM, AROM, adapted ASES function subscale, and adapted ASES pain subscale.

For the Investigator Satisfaction with Treatment and Subject Satisfaction with Treatment at the Days 64 and Day 95 Visits, a Wilcoxon rank sum nonparametric test will be performed to compare active to placebo. A Wilcoxon rank sum nonparametric test will also be used to compare active to placebo for the change from baseline in Patient-reported Global Severity of Adhesive Capsulitis at the Day 22, 43, 64 and 95 Visits.

For Patient-reported Change in Severity of Adhesive Capsulitis at the Day 22, 43, 64, and 95 Visits, a chi-square test will be performed to compare active to placebo.

Endpoints of the affected shoulder in the EN3835 group will be compared to the endpoints of the affected shoulder in the placebo group.

The tertiary/exploratory analysis plan will be provided in the SAP.

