3.15.4.1. Patient-reported Change in Severity of Adhesive Capsulitis

The Patient-reported Change in Severity of Adhesive Capsulitis is a questionnaire that asks subjects if their AC symptoms are "Better, About the Same, or Worse" since the last time the questionnaire was administered.

Subjects who report that their symptoms are better or worse are then asked to rate the change in their symptoms on a 7-point ordinal scale.

			Responses
No.	Question	Numeric	Description
1	Have there been any changes in overall severity of	-1	Worse (Complete Question 2)
	your frozen shoulder since you started the study?	0	About the same (Stop)
		1	Better (Complete Question 3)
2	How much worse would you say the overall severity of	0	Almost the same, hardly worse at all
	your frozen shoulder is since you started the study?	-1	A little worse
		-2	Somewhat worse
		-3	Moderately worse
		-4	A good deal worse
		-5	A great deal worse
		-6	A very great deal worse
3	How much better would you say the overall severity of	0	Almost the same, hardly better at all
	your frozen shoulder is since you started the study?	1	A little better
		2	Somewhat better
		3	Moderately better
		4	A good deal better
		5	A great deal better
		6	A very great deal better

 Table 8:
 Patient-reported Change in Severity of Adhesive Capsulitis Scale

All subjects will complete the Patient-reported Change in Severity of Adhesive Capsulitis questionnaire at times outlined in the SoA (Table 2).

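### The ordered Patient-reported Change in Severity responses are compared with a test that ignores their order, and the SAP does not say whether the graded -6 to +6 rating is compared at all

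*SAP*

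**What the plan says.** SAP Section 3.15.4.1 and Table 8 define the instrument. Question 1 has three ordered answers coded -1, 0 and +1 (worse, same, better). Subjects who answer worse or better are "then asked to rate the change in their symptoms on a 7-point ordinal scale", coded 0 to -6 for worse and 0 to +6 for better.

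SAP Section 7.9.2.6 states the comparison: responses at each of the four visits "will be compared between EN3835 to placebo using a chi-square test", or Fisher's exact test, depending on the expected frequencies. The null hypothesis is general independence: "The distribution of responses is independent of the treatment groups". The alternative names no direction or ordering. A separate sentence then adds: "The change in the symptoms will be summarized by each treatment group using frequency counts and percentages with mean and SD". No test is attached to that sentence.

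Protocol Section 9.3.1 agrees on the method: "a chi-square test will be performed to compare active to placebo". SAP Table 17, which lists departures from the protocol, has no entry for this endpoint.

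The other ordinal secondary endpoints are handled differently. For Global Severity, SAP Section 7.9.2.5 says: "A Wilcoxon rank sum nonparametric test will be used to compare EN3835 to placebo for the change from baseline in Patient-reported Global Severity". Sections 7.9.2.7 (Investigator Assessment) and 7.9.2.8 (Subject Satisfaction) use the same test, as does Section 7.9.2.2 for the ranked hand-behind-back values.

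**The concern.** A Pearson chi-square or Fisher test gives the same p value however the columns are arranged, so it does not concentrate power on a shift toward improvement. On an ordered scale, that shift is what a treatment benefit would look like.

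The wording also leaves the tested variable open. If it is Question 1, subjects who are slightly better and subjects who are very greatly better count the same, and the grading is never compared between arms. If it is the full rating, the chi-square spreads its power over up to 12 degrees of freedom with small cells. Neither document explains why this scale is treated as nominal when the Investigator Assessment, a seven-level signed improvement scale of similar form, gets a rank test.

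At stake is the power of a listed secondary endpoint at four visits, using data the trial already collects.

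**Working it through.** **Inputs from the documents.** Two-sided alpha 0.05 (SAP 6.1). Mean changes 38.6 and 27.6, SD 21.6, 1:1 allocation, power 85%, 142 completers, 180 dosed (protocol 9.1, SAP 3.5). All of these describe the adapted ASES composite, not this scale.

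**The plan's own figure.** Standardized effect = (38.6 - 27.6)/21.6 = 11.0/21.6 = 0.509.

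- Normal approximation: n per arm = 2 x (1.960 + 1.036)^2 x 21.6^2/11.0^2 = 2 x 8.98 x 3.856 = 69.2, so 70.
- t-test: 70.2, so 71 per arm, or 142 in total, as stated. Power at 71 per arm is 85.4%.
- Dropout: 142/(1 - 0.20) = 177.5, so 178, against 180 planned.

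The sample size reproduces. No corresponding figure exists for Patient-reported Change in Severity, so the rest rests on assumptions.

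**Assumptions for the comparison.** 71 per arm. A normal latent response, shifted upward in the active arm. Cut points are set from assumed placebo shares (worse/same/better) of 20/30/50, 10/20/70 and 5/15/80 percent. The worse and better parts are each split into six grades of equal placebo probability, which with zero makes 6 + 1 + 6 = 13 levels. There were 2,000 simulated trials per scenario, so the standard error is at most sqrt(0.25/2000) = 1.1 points.

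| Shift (SD) | Placebo Better | Chi-square, 3 levels | Wilcoxon, 3 levels | Chi-square, 13 levels | Wilcoxon, -6 to +6 |
|---|---|---|---|---|---|
| 0.509 | 50% | 61.5% | 71.0% | 36.5% | 82.7% |
| 0.509 | 70% | 48.5% | 58.7% | 36.1% | 82.2% |
| 0.509 | 80% | 36.5% | 48.0% | 38.9% | 82.4% |
| 0.40 | 50% | 39.9% | 50.5% | 23.5% | 61.8% |
| 0.40 | 70% | 31.7% | 41.4% | 21.1% | 63.9% |
| 0.40 | 80% | 24.8% | 32.5% | 24.1% | 60.6% |
| 0.30 | 50% | 25.9% | 33.0% | 12.0% | 41.0% |
| 0.30 | 70% | 20.1% | 27.7% | 11.8% | 40.4% |
| 0.30 | 80% | 15.7% | 22.3% | 12.7% | 39.0% |

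Independent repeat runs agreed to within about 3 points. Null runs put the Wilcoxon type I error between 3.9% and 5.9%, consistent with 5% within simulation error.

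**Splitting the gain at 0.509 SD.**

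- Using order on the same three levels adds 71.0 - 61.5 = 9.5, 58.7 - 48.5 = 10.2 and 48.0 - 36.5 = 11.5 points.
- Moving from three levels to the graded score adds a further 82.7 - 71.0 = 11.7, 82.2 - 58.7 = 23.5 and 82.4 - 48.0 = 34.4 points.

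So about 10 points come from respecting order. The rest comes from using the grading, and that part grows as more placebo subjects report improvement.

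**Dependence on the grade split.** With unequal splits of the better grades (ceiling-heavy or clustered) at 0.509 SD, Wilcoxon on the graded score had 75% to 85% power. The three-level chi-square had 34% to 69% and the 13-level chi-square 30% to 40%. The ranking does not depend on one choice of cut points. Fisher's exact test was not simulated; it also ignores order.

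**The case against.** The chi-square test is valid and is specified consistently in both documents. This is one of many secondary endpoints in a Phase 2 study, with no power claim of its own. A closely related patient rating, Global Severity, is already compared by Wilcoxon at the same four visits. All of this stands, and it limits the point to lost efficiency.

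A reader might infer three stronger things that the documents do not support.

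- **That the graded rating is certainly never tested.** Section 7.9.2.6 does not define which responses enter the test. The separate descriptive sentence echoes the wording used for the graded rating in Section 3.15.4.1. That favours the Question 1 reading but does not settle it.
- **That a significant result would carry no direction.** The p value alone carries none, but the same section reports percentages by arm and the mean and SD of the change, from which direction can be read.
- **That the test would miss a benefit of the size the trial was designed to detect.** The design effect of 0.51 SD belongs to the ASES composite in a post hoc MRI subgroup of an earlier study. Nothing ties it to this scale. At 0.30 SD even the rank test reaches only about 40%.

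**Conclusion.** The point holds as a loss of efficiency together with an unclear specification. The planned test ignores order under either reading of the text, and no other section applies a rank or trend test to this endpoint.

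Under the assumptions above, with 50% to 80% of placebo subjects Better, the graded Wilcoxon exceeds the three-level chi-square by 82.7 - 61.5 = 21 to 82.4 - 36.5 = 46 points at 0.51 SD. At 0.30 SD the gap is 41.0 - 25.9 = 15 to 39.0 - 15.7 = 23 points. If the chi-square is meant to cover all 13 levels, its power is only about 36% to 39% at 0.51 SD and 12% to 13% at 0.30 SD.

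These sizes depend on an assumed effect and assumed category shares; the direction was the same in every scenario tried. There is no bias, and the primary analysis and sample size are untouched. The change is worth making but is not critical.

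**What to change.** Before unblinding, revise SAP Section 7.9.2.6 as follows.

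- Define one score from Questions 1 to 3 of Table 8, running from -6 to +6. Set the about-the-same answer to Question 1 to 0, and likewise the hardly-changed grades that Questions 2 and 3 already code 0.
- Compare arms on this score at each visit with the Wilcoxon rank sum test, as in Section 7.9.2.5.
- Keep the Better/Same/Worse frequencies as a descriptive table.
- Record the departure from protocol Section 9.3.1 in SAP Table 17.

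The recall period should be reconciled in the same revision, because the meaning of the score depends on it. The text of SAP Section 3.15.4.1 and protocol Section 8.1.4.1 refers to the previous administration of the questionnaire, while the Table 8 items refer to the start of the study.

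The cost is SAP wording and one changed procedure call, with no new data. The small downside is a documented change from the test the protocol names. Using Table 17 avoids a protocol amendment, which under protocol Section 10.1.1 would need ethics committee approval.

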7.9.2.7. Investigator Assessment of Improvement with Treatment

A Wilcoxon rank sum nonparametric test will be used to compare EN3835 to placebo for the Investigator Assessment of Improvement with Treatment in the affected shoulder at the Day 64 and 95 Visits.

The null and alternative hypotheses for this test will be as below:

H₀: There is no difference in the Investigator Assessment of Improvement with Treatment in the 2 treatment groups.

Vs

H₁: The Investigator Assessment of Improvement with Treatment differs in the 2 treatment groups.

Wilcoxon scores (Rank Sums) for treatment group and test statistics along with p value for the test of significance will be presented.

Reponses for Investigator Assessment of Improvement with Treatment in the affected shoulder and responders will be summarized by treatment group using frequency counts and percentages with mean and SD.

A listing of Investigator Assessment of Improvement with Treatment scores will be provided.

7.9.2.8. Subject Satisfaction with Treatment

A Wilcoxon rank sum nonparametric test will be used to compare EN3835 to placebo for all the individual questions of Subject Satisfaction prior to receiving treatment and Subject Satisfaction compared to better shoulder for the affected shoulder at the Day 64 and 95 Visits. The null and alternative hypotheses for this test will be as below:

H₀: There is no difference in the Subject Satisfaction with Treatment in the 2 treatment groups.

Vs

H₁: Subject Satisfaction with Treatment differs in the 2 treatment groups.

Wilcoxon scores (Rank Sums) for treatment group and test statistics along with p value for the test of significance will be presented.

Reponses for Subject Satisfaction with Treatment in the affected shoulder and responders will be summarized by treatment group using frequency counts and percentages with mean and SD.

A listing of Subject Satisfaction with Treatment scores will be provided.

7.9.3. Exploratory/Tertiary Analyses

7.9.3.1.

7.9.4. Sensitivity Analysis

7.9.4.1. Primary Endpoint Sensitivity Analysis with MMRM using Tipping Point Analysis (TPA)

A sensivity analysis will be performed to assess the impact of missing data with MMRM using tipping point analysis as described in section 7.9.1. Note that if the primary analysis result is not significant (p-value greater than 0.05), no sensitivity analysis will be performed.

To evaluate the impact of deviations from the missing at random (MAR) assumption, a deltaadjustment multiple imputation (MI) method will be used to find the tipping point where the result is no longer statistically significant.

There are three steps to be followed for this sensivity analysis.

Step 1: Generate Pattern of Missing Data

Before various MI methods are applied, the different types of missing data patterns will be checked using NIMPUTE=0 in SAS PROC MI. This will generate the pattern of missing data and will not generate any imputed values for missing data.

PROC MI DATA=*INPUT* NIMPUTE=0; VAR *VAR1 VAR2 VAR3...(variables in order the missing patterns are created for)*; RUN;

Step 2: Imputation of data for non-monotone and monotone missing data

• Intermittent missing values: If there are subjects with intermittent missing values (ie. non-monotone missing data), the intermittent missing values will be imputed based on Markov Chain Monte Carlo (MCMC) methods. SAS PROC MI will be utilized with MCMC to generate datasets with monotone missing pattern. The number of imputations will be set to *n* (20 is the default value).

PROC MI DATA=*INPUT* NIMPUTE=*n* SEED=234 OUT=*IN_MCMC*; VAR ...; (treatment group, baseline covariates, and the preceding non-missing values in the order of clinical visits: baseline, Visit X, ..., Visit Y) MCMC CHAIN=SINGLE NBITER=1000 NITER=1000 IMPUTE=MONOTONE; RUN;

- If all subjects have a monotone missing data pattern (either directly from the study or created by the previous step), the MAR-based multiple imputation with the regression option will be used to impute missing values, the imputed values will then be adjusted accordingly. Delta-adjustment will be generated for different combinations of δ_P an δ_A values as defined below:
 - Active-only adjustment analysis: $\delta_P = 0$ and $\delta_A = 0$ to Δ_1 (Δ_1 is the effect size reported in the primary analysis)
 - Analysis with a control adjustment that is half of the active adjustment: $\delta_P = \delta_A / 2$ and $\delta_A = 0$ to Δ_1
 - All arms with identical adjustment: $\delta_P = \delta_A$ and $\delta_A = 0$ to Δ_1
- The imputation will be performed using SAS PROC MI with the MONOTONE statement and the REGRESSION option with the following specifications:

```
PROC MI DATA=IN_MCMC NIMPUTE=1 (see note) SEED=234 OUT=OUTPUT;
VAR ...; (treatment group, baseline covariates, and the preceding non-missing values in
the order of clinical visits: baseline, Visit X, ..., Visit Y)
CLASS...; (treatment group)
MONOTONE REG (/details);
MNAR ADJUST (Visit X / SHIFT=delta_a ADJUSTOBS=(TRT01PN ='1'));
MNAR ADJUST (Visit Y / SHIFT=delta_a ADJUSTOBS=(TRT01PN ='1'));
MNAR ADJUST (Visit Y / SHIFT=delta_a ADJUSTOBS=(TRT01PN ='1'));
MNAR ADJUST (Visit X / SHIFT=delta_a ADJUSTOBS=(TRT01PN ='1'));
MNAR ADJUST (Visit X / SHIFT=delta_p ADJUSTOBS=(TRT01PN ='0'));
MNAR ADJUST (Visit Y / SHIFT=delta_p ADJUSTOBS=(TRT01PN ='0'));
MNAR ADJUST (... / SHIFT=delta_p ADJUSTOBS=(TRT01PN ='0'));
```

Note: NIMPUTE=n if MCMC was NOT applied at the previous step.

Step 3: Analysis and Pooling

For each value of δ_P and δ_A , MMRM described in section 7.9.1 will be performed for each of the n adjusted fully imputed datasets. The analysis results obtained will be combined into a single estimation using PROC MIANALYZE to produce final inferences.

The following estimates will be presented in the sensitivity analysis table:

- 1. LSM estimate for the mean change from baseline at the visit where primary endpoint is measured for each treatment.
- 2. LSM estimate for treatment difference of the mean change from baseline at the visit where primary endpoint is measured and the corresponding 2-sided 95% CI and p-value for change from baseline in the primary endpoint will be provided.

Shift parameters will begin with active-only adjustment, followed by a control adjustment that is half of the active adjustment, followed by all arms with identical shift adjustments, as stated in Step 2.

25-April-2022

All steps above are repeated with different values of the shift parameter until the tipping point is reached or all possible values are explored. The tipping point can be identified when the result is no longer statistically significant (p-value >0.05). It is possible a tipping point is not reached if little to no data is missing.

Once tipping point is reached, if implausible departure from MAR is needed to change the results from statistically significant to insignificance, the results of the primary endpoint are considered to be robust. If the tipping point obtained for overturning the primary endpoint result is clinically plausible, the conclusion can be questioned and viewed with caution.

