4.7.1.3. Composite Score

The adapted ASES composite score is the sum of the pain subscale score (50% of the composite score) and the function subscale score (50% of the composite score). The calculation is:

Composite score = Pain subscale score + Function subscale score

25-April-2022

The range for the composite score is 0-100, where 0 is the worst pain and least functional and 100 is least pain and most functional. If either of the pain subscale or function subscale score is missing, then the ASES composite score will be considered as missing.

Change from baseline in the adapted ASES composite score for the affected shoulder at the Day 22, 43, 64, and 95 Visits will be analyzed. Positive change from baseline score means an improvement in pain and/or shoulder function from baseline.

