7.9.1. Primary Analysis

7.9.1.1. Change from Baseline in Adapted ASES Composite Score

The primary endpoint is the change from baseline to the Day 95 Visit in the adapted ASES composite score.

MMRM will be performed to estimate change from baseline treatment effect at Day 64 and Day 95 Visits comparing active to placebo for the adapted ASES composite score in the affected shoulder. MMRM will be performed to estimate the least square (LS) means of change from baseline for EN3835 and placebo treatment. *P* values and 95% CIs for the treatment difference (EN3835 – Placebo) will be calculated by MMRM for the visits with treatment, visit, and an interaction of treatment and visit as fixed effected and repeated with visit/subject. Autoregressive covariance structure will be used in the model.

Observed values and change from baseline in the adapted ASES composite score in the affected shoulder for each treatment group will be summarized at Day 22, 43, 64 and 95 Visits using descriptive statistics.

A listing of adapted ASES scores will be provided.

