8. CHANGE FROM PROTOCOL

This SAP is prepared based on the study protocol; original version dated April 06, 2020, Amendment 1 dated July 10, 2020, Amendment 2 dated July 31, 2020, Amendment 3 on November 06, 2020, and Amendment 4 on October 22, 2021.

Table 17 lists any significant changes in the SAP from what is proposed in the protocol.

Text in Protocol	Change in SAP	Justification
The Per-Protocol (PP) Population is defined as those subjects in the mITT Population who do not have any major protocol deviations.	The PP Population is defined as those subjects in the mITT Population who do not have any major protocol deviations which have a significant effect on the primary endpoint.	Change the PP Population to emphasize only subjects with major PDs that effect the primary endpoint to be excluded. This allows subjects with major PDs related to safety only (and no effect on primary endpoint) to be included in PP Population.
N/A	Added a tipping point sensitivity analysis (section 7.9.4)	Tipping point analysis checks if the missing data effects the primary analysis conclusions by checking severity of missing data. Identify the tipping poing where treatment effect in subjects with missing data overturns the significant treatment effect otbtained in the missing at random primary analysis.

Table 17:Changes from Protocol

9. **REVISION HISTORY**

Non-editorial changes made to any of the modules of this SAP will be recorded in Table 18.

Table 18:Revision History

Version	Date	Revision Author	Comments
v1.0	Aug 12, 2020		Original version
v2.0	April 25, 2022		Protocol amendment updates, prior/concomitant definition, adverse events of special interest, tipping point sensitivity analysis

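### As printed, the tipping-point shift raises imputed EN3835 scores after a favourable result, so its main scenario cannot find the point where significance is lost

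*SAP*

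**What the plan says.** SAP 7.9.4.1 imputes missing composite scores under MAR, shifts them by delta_A on EN3835 and delta_P on placebo, and refits the primary model. Three scenarios are run in order:

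- active-only: "Active-only adjustment analysis: $\delta_P = 0$ and $\delta_A = 0$ to Δ_1";
- half-control: delta_P is half of delta_A;
- identical: delta_P equals delta_A.

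In each, delta_A runs from 0 to Delta_1, which "is the effect size reported in the primary analysis". The code for the active arm reads "SHIFT=delta_a ADJUSTOBS=(TRT01PN ='1", without a minus sign.

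Two other sections fix the direction. SAP 4.7.1.3 says of the composite: "Positive change from baseline score means an improvement in pain and/or shoulder function from baseline". SAP 7.9.1.1 gives p-values and intervals "for the treatment difference (EN3835 – Placebo) will be calculated by MMRM".

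Table 17 in SAP 8 states the purpose: "Identify the tipping poing where treatment effect in subjects with missing data overturns the significant treatment effect". For a search that fails, SAP 7.9.4.1 says only: "It is possible a tipping point is not reached if little to no data is missing". Its closing rule on plausibility applies once a tipping point has been reached. The whole analysis is skipped if the primary p-value exceeds 0.05.

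**The concern.** A tipping-point analysis should make the treated dropouts progressively worse than MAR predicts, until significance is lost. Here a favourable Delta_1 is positive, the shift runs from zero up to it, and it is added. Neither document says that delta is negative, a decrement or a penalty. Followed as written, the plan makes EN3835 dropouts progressively better. None of the three scenarios asks whether they did worse than MAR predicts.

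The primary result cannot change, because the analysis runs only after significance. What is at stake is how far that result is trusted. The plan expects about 20% drop-out, and Amendment 4 enlarged the trial because early termination exceeded expectation. If no tipping point is found, the one explanation the SAP offers is that little data is missing, yet a wrong sign would give the same outcome.

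**Working it through.** **Inputs.** From SAP 3.5: mean changes of 38.6 and 27.6 (difference 11.0), SD 21.6, 90 per arm dosed, 142 of 180 completing. That leaves 38/180 = 21.1% without Day 95, or 19 of 90 per arm if evenly split. From SAP 6.1: two-sided alpha 0.05. Missingness by arm is not given, so 10% to 30% is assumed.

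**The plan's own figure.** 2 × (1.960 + 1.036)² × (21.6/11.0)² = 69.2, so 70 per arm. The t-based solution is 71 per arm, or 142, which matches. 142/0.80 = 177.5, against 180 stated. The effect and SD can be used as they stand.

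**Formula.** With missing fractions mA (EN3835) and mP (placebo), and an unshifted difference D:

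- shifted difference = D + mA·delta_A − mP·delta_P
- variance = 21.6²/[90(1−mA)] + 21.6²/[90(1−mP)] + mA(1−mA)·delta_A²/90 + mP(1−mP)·delta_P²/90

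At the full printed shift (delta_A = D, delta_P = kD) the difference is D(1 + mA − k·mP), with k = 0, 0.5 or 1 for active-only, half-control and identical. Active-only is therefore always above D. Half-control falls below D only if mP > 2mA, and identical only if mP > mA.

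**Worked case, 21.1% missing in each arm.** Unshifted SE = 21.6 × √(2/71) = 3.625. For active-only at D = 11.0, the difference is 11.0 + 0.211 × 11.0 = 13.3 and SE = √(13.143 + 0.211 × 0.789 × 121/90) = 3.656, so z = 3.64. D = 7.3 serves as a just-significant result.

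| Full shift | D = 11.0, printed | D = 7.3, printed | D = 11.0, reversed | D = 7.3, reversed |
|---|---|---|---|---|
| none | 11.0, p 0.0024 | 7.3, p 0.044 | same | same |
| active-only | 13.3, p 0.0003 | 8.8, p 0.015 | 8.7, p 0.018 | 5.8, p 0.11 |
| half-control | 12.2, p 0.0009 | 8.1, p 0.027 | 9.8, p 0.007 | 6.5, p 0.073 |
| identical | 11.0, p 0.003 | 7.3, p 0.046 | 11.0, p 0.003 | 7.3, p 0.046 |

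**Unequal missingness, printed sign.** With 30% missing on EN3835 and 10% on placebo, the multipliers of D are 1.30, 1.25 and 1.20, so all three scenarios favour EN3835. With 10% and 30% they are 1.10, 0.95 and 0.80. The last two can tip, but only because placebo values were raised.

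**Which results can tip at the Delta_1 cap.** With the printed sign, identical-shift tips primary p-values above 0.048 at 20/20 and above 0.013 at 10/30 (EN3835/placebo %). With the sign reversed, active-only tips p-values above 0.029, 0.014 or 0.005 at 10%, 20% or 30% missing in each arm.

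**Simulation.** Each pattern had 400 trials, 90 per arm, true effect 11, SD 21.6, four post-baseline visits, assumed AR(1) correlation 0.6, random monotone dropout after Day 22, 20 sequential-regression imputations and Rubin pooling of the Day 95 difference. The percentages are of significant trials that tipped under active-only.

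| Missing %, EN3835/placebo | Significant trials | Printed | Reversed | Reversed, shift carried into later visits |
|---|---|---|---|---|
| 10/10 | 361 | 0 | 4.7 | 9.4 |
| 20/20 | 329 | 0 | 17.3 | 35.3 |
| 30/30 | 327 | 0 | 35.8 | 76.8 |
| 30/10 | 337 | 0 | 31.2 | 72.1 |
| 10/30 | 332 | 0 | 4.8 | 10.2 |

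In all 1,686 significant trials the printed active-only shift raised the estimate. Half-control as printed tipped none, except 1.8% at 10/30. Identical-shift as printed tipped 0 to 1.2% at equal missingness, 0% at 30/10 and 16.6% at 10/30. With carry-over, printed active-only stays at 0%, half-control reaches 3.9% at 10/30, and identical-shift is 0.3% to 3.1% at equal missingness and 36.7% at 10/30.

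**The case against.** The strongest reply is that the intent is plain. The section sets out to find where significance is lost, the code is a template with placeholders, and a programmer would know to subtract. The intent was probably a penalty. But the SAP prints the range and the code line and nowhere defines delta as a decrement, so a programmer and a validator who follow it would agree on the wrong sign.

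A second reply is that the error would show. The planned table gives both LS means, the difference, the interval and the p-value, and a rising difference should be noticed. That is a real safeguard, and the table shells in SAP Module 2, which were not available, may add more. It depends on someone noticing, though, and the sentence on little missing data offers a harmless explanation for a failed search.

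Three limits stand:

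- If placebo were significantly better, Delta_1 would be negative and the shift would lower EN3835 scores. The point concerns favourable results.
- When placebo loses many more subjects, the printed plan is stricter in one respect. At 10/30 its identical-shift scenario tips 16.6%, against 4.8% for reversed active-only. Reversing the sign turns the half-control and identical multipliers there into 1.05 and 1.20. Those printed tips come from favouring placebo dropouts and do not test EN3835 dropouts.
- The simulated percentages compare Day 95 means in place of the planned repeated-measures fit and are illustrative.

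That this is a conditional sensitivity analysis in a Phase 2 trial bears on consequence. It does not make the printed rule right.

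**Conclusion.** The point holds. After a favourable primary result, no printed scenario lowers an imputed EN3835 score, and active-only can only enlarge the difference: by 10%, 20% or 30% of Delta_1 at 10%, 20% or 30% missing on EN3835. The weakness is worst when EN3835 loses more subjects than placebo, because all three scenarios can then move in its favour.

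The direction needs only the printed scale, the printed contrast and the reading of SHIFT as an added constant. The sizes rest on assumed missingness by arm, and the simulated rates also on the assumed correlation of 0.6 and random dropout. The sign should be corrected before database lock, since this is the only planned test of departures from MAR for the primary endpoint.

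**What to change.** In SAP 7.9.4.1:

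- State that imputed EN3835 values are shifted downward, for example SHIFT = −delta_a with delta_a ≥ 0. Put placebo on the same convention, with delta_p equal to 0, delta_a/2 or delta_a.
- State whether a shifted value at one visit feeds the imputation of later visits. The simulation shows that this changes the tipping rate by a factor of about two.
- State that a search with no tipping point is reported with the range explored and the estimate, interval and p-value at its end, and is not put down by default to little missing data.

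As a separate recommendation, let delta_a run past Delta_1 until p exceeds 0.05 or the 0–100 scale limit is reached. Without that, even the corrected active-only search cannot tip a primary p-value below about 0.014 at 20% missing, unless shifts carry over.

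The cost is a few lines of text and code before database lock and no new data. The sensitivity result may look less favourable.
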